# STUDY DISCONTINUATION

A study participant may elect to discontinue participation in the study at any time. The study may be discontinued at any time by the IRB, the OHRP, or other government agencies as part of their duties to ensure that research subjects are protected.

# **BIOHAZARD CONTAINMENT**

Blood-borne pathogens can occur through contact with contaminated needles, blood, and blood products. Appropriate blood and secretion precautions will be employed by all personnel in the drawing of blood and handling of all specimens for this study, as currently recommended by the Centers for Disease Control and Prevention and the National Institutes of Health. All infectious specimens will be transported using packaging mandated in the Code of Federal Regulations, 42 CFR Part 72.

### **BIOSAFETY PLAN**

No specific biosafety plan is necessary for this protocol as all planned immunologic and genetic assays will fall under the existing biosafety protocols of the Hope Clinic and CDC.

Unique Protocol ID: IRB00092488

NCT02985996

Statistical Analysis Plan

Truvada® vs. Genvoya®

Principal Investigator [name] [name]

01/15/2019

Demographic, behavioral, clinical, and laboratory data will be collected from the screening clinical assessment, the study entry physical examination and screening laboratory tests, and rectal biopsy visits.

Median (range) drug levels will be calculated at baseline and each of the protocol specified follow-up time points. Differences in median drug levels between baseline and study visit follow-up visits will be analyzed with non-parametric Wilcoxon-signed rank tests. A p-value of <0.05 will be considered significant.

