men will be screened for eligibility and will undergo the informed consent process. Once informed consent is signed, a physical examination will be performed, rapid HIV testing, phlebotomy for screening labs, and randomization will occur. During study visit 2 (time 1-6 weeks after study visit 1), men will be dispensed and instructed to take either Truvada® or Genvoya® for 10 days. After 3 to 5 consecutive days of dosing, participants will return for visit 3 where a urethral and penile swabs specimen, blood work, and a urine specimens will be obtained. During study visit 4 (time 10 days of consecutive drug dosing), men will return for repeat phlebotomy, urethral and penile swabs, collection of urine and rectal secretions, and rectal biopsy. After collection, biologic specimens will be immediately transported by courier to CDC (laboratory of [name]) for processing. Specimens will be processed immediately for ex vivo laboratory assays that will include Truvada® and/or Genvoya® drug concentrations, inflammatory cytokine levels, HIV target cell measurement and characterization by flow cytometry, and in vitro HIV infection assays. Comparison of assay results between the 2 study arms will help in determining the ability of the new formulated anti-HIV drug to penetrate different body compartments at the site of possible HIV exposure.

Participants may participate in more than one phase; however, at least 8 weeks must lapse after completion of 1 study phase before entry into another. Men who participate in more than one phase will not be consented again and do not have to repeat the screening visit (visit 1) when starting another phase; they will begin the new phase at visit 2.

Duration: The duration of this study is 3 years. Participants will be considered 'on-study' for no more than 12 weeks.

Sample size: For this protocol we will recruit 90 HIV-negative MSM or transgender women who are not taking hormone therapy who meet eligibility criteria outlined in the protocol.

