# PROJECT DESCRIPTION

**Public Health Relevance:** Information about new anti-HIV agents and how they penetrate through mucosal tissues will better inform scientists about the potential of new agents to be used for pre-exposure prophylaxis (PrEP).

**Goal**: To compare the body compartment pharmacokinetics and mucosal inflammatory effects of Truvada® vs. Genvoya®.

Version 6 04/21/17

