# **INCLUSION CRITERIA FOR MSM**

- 1) HIV-negative man who reports receptive anal sex with another man in the last 6 months
- 2) Male to female transgender women who have sex with men who report receptive anal intercourse with another man in the last 6 months and are not currently taking hormonal therapy or plan to take hormonal therapy for the duration of the study
- 3) Aged 18-49 years
- 4) Not currently taking PrEP and no plans to initiate during study
- 5) Able to provide informed consent in English
- 6) No plans for relocation in the next 3 months
- 7) Willing to undergo peripheral blood and rectal biopsy sampling
- 8) Willing to use study products as directed
- 9) Willing to abstain from receptive anal intercourse 3 days prior to starting study product and for the duration of the study and for 7 days after any rectal biopsy procedure.

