# EXCLUSION CRITERIA

- History of inflammatory bowel disease or other inflammatory, infiltrative, infectious or vascular condition involving the lower gastrointestinal tract that, in the judgment of the investigators, may be worsened by study procedures or may significantly distort the anatomy of the distal large bowel
- 2) Significant laboratory abnormalities at baseline visit, including but not limited to:
  - a) Hgb  $\leq$  10 g/dL
  - b) PTT > 1.5x ULN or INR > 1.5x ULN
  - c) Platelet count <100,000
  - d) Creatinine clearance <60

- Any known medical condition that, in the judgment of the investigators, increases the risk of local or systemic complications of endoscopic procedures or pelvic examination, including but not limited to:
  - a) Uncontrolled or severe cardiac arrhythmia
  - b) Recent major abdominal, cardiothoracic, or neurological surgery
  - c) History of uncontrolled bleeding diathesis
  - d) History of colonic, rectal, or vaginal perforation, fistula, or malignancy
  - e) History or evidence on clinical examination of ulcerative, suppurative, or proliferative lesions of the anorectal or vaginal mucosa, or untreated sexually transmitted disease with mucosal involvement
- 4) Continued need for, or use during the 14 days prior to enrollment, of the following medications:
  - a) Aspirin or more than 4 doses of NSAIDs
  - b) Warfarin, heparin (low-molecular weight or unfractionated), platelet aggregation inhibitors, or fibrinolytic agents
  - c) Any form of rectally administered agent besides products lubricants or douching used for sexual intercourse
- 5) Continued need for, or use during the 90 days prior to enrollment, of the following medications:
  - a) Systemic immunomodulatory agents
  - b) Supraphysiologic doses of steroids
  - c) Experimental medications, vaccines, or biologicals
- 6) Intent to use HIV antiretroviral pre-exposure prophylaxis (PrEP) during the study, outside of the study procedures
- 7) Symptoms of an untreated rectal sexually transmitted infection (e.g. rectal pain, discharge, bleeding, etc.)
- 8) Current use of hormonal therapy
- 9) Any other clinical condition or prior therapy that, in the opinion of the investigator, would make the patient unsuitable for the study or unable to comply with the study requirements.

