# Visit 1

# Phase I, II, and III

During the screening visit, eligible MSM will provide written informed consent after all their questions are answered in a private exam room at the Hope Clinic. Subjects will also receive an approved HIPAA statement and will be informed about the way their protected health information will be used and stored. Copies of the consent/HIPAA form for this project will not be placed in individuals' medical records since this study collects sensitive information such as HIV status and sexual orientation.

After provision of informed consent, a medical history and physical examination will be conducted by the PI to evaluate for exclusion criteria. A rapid HIV test with finger stick whole blood (Determine or other CLIA waved product) will be performed by the PI or study coordinator who will be certified in HIV counseling and testing to confirm eligibility. Peripheral blood will be drawn for a complete blood count, creatinine, and coagulation tests.

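### The SAP plans no Truvada v Genvoya estimate and gives the screening data no role; specify the arm comparison and say whether screening creatinine clearance enters it

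*SAP*

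**What the plan says.** The SAP has two short paragraphs of content. The first lists what is gathered: "Demographic, behavioral, clinical, and laboratory data will be collected from the screening clinical assessment", together with the entry examination and the biopsy visits. The second is the whole analysis. It gives the median and range of drug levels at each time point, and one test: "Differences in median drug levels between baseline and study visit follow-up visits will be analyzed with non-parametric Wilcoxon-signed rank tests". The threshold is "A p-value of <0.05 will be considered significant", with sidedness not stated. No arm comparison and no covariate is named; the two drugs appear together only in the SAP's title.

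The protocol's Project Description gives the goal: "To compare the body compartment pharmacokinetics and mucosal inflammatory effects of Truvada" against Genvoya. The Abstract adds: "Comparison of assay results between the 2 study arms will help in determining the ability of the new formulated anti-HIV drug" to reach the relevant body compartments. Neither place gives a statistical method.

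On the screening data, the protocol's Visit 1 section, which covers all three phases, says: "Peripheral blood will be drawn for a complete blood count, creatinine, and coagulation tests". The Exclusion Criteria list "Creatinine clearance <60", without a unit or formula. Clearance must therefore be known for each man before he is dosed.

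**The concern.** The trial randomises men between two drugs in order to compare them, yet the one planned test asks whether a participant's level after dosing differs from his own level before it. A signed-rank test of that kind can show that drug is detectable. It cannot say how much higher or lower one arm is than the other in any compartment.

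If the between-arm analysis is first written after the data are seen, the choice of analyte, compartment, time point, scale and covariates becomes post hoc. The groups are small (20 per arm in each dosed phase, fewer after drop-out), so it is also worth deciding in advance whether a value already measured at screening could sharpen the comparison.

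**Working it through.** **1. What the SAP would deliver.** The goal is a contrast between arms. The planned test is a contrast within participants over time. A characteristic fixed at screening is not a missing term in that test, so the first gap is the absent arm comparison; the covariate question comes second.

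**2. The only figure that can be reproduced.** The Study Population section expects about 20% of 90 men not to complete, leaving 72: 90 × 0.80 = 72, which agrees. The phases add up: 10 + 40 + 40 = 90. Phases II and III have 20 men per arm, so about 20 × 0.80 = 16 completers per arm per phase. Phase I (5 per arm) receives no drug and offers no drug-level contrast. The documents give no power, effect size or variability.

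**3. Assumed inputs (none is in the documents).**
- Log drug-level SD: 0.7.
- Log creatinine-clearance SD: 0.15 to 0.25.
- Level inversely proportional to clearance, so r = SD(log clearance) / SD(log level).
- True ratio of 2 between arms; two-sided alpha 0.05; n = 16 per arm (N = 32).

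**4. Range of r.** 0.15/0.7 = 0.21 and 0.25/0.7 = 0.36, so R² = r² runs from 0.046 to 0.128.

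**5. Effect of adjustment on variance.** With one covariate the expected variance of the arm difference is multiplied by

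(1 − R²) × (N − 3)/(N − 4) = (1 − R²) × 29/28,

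and one error degree of freedom is lost (30 to 29). The factor 29/28 = 1.036 is the average price of estimating the covariate slope.
- Break-even at n = 16: R² = 1 − 28/29 = 0.034.
- Break-even at n = 20 (N = 40): R² = 1 − 36/37 = 0.027.

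**6. Power (noncentral t).** The unadjusted standard error is 0.7 × √(2/16) = 0.247, and log 2 = 0.693.

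| Analysis | R² | Variance factor | Power |
|---|---|---|---|
| Unadjusted | – | 1 | 77.3% |
| Adjusted, r = 0 | 0 | 1.036 | 75.8% |
| Adjusted, r = 0.21 | 0.046 | 0.988 | 77.7% |
| Adjusted, r = 0.36 | 0.128 | 0.904 | 81.3% |

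The gain is 0.4 to 4.0 points across the assumed range. In equivalent sample size it is 1/0.988 to 1/0.904, about 1% to 11% more men. With no relation, the loss is about 1.5 points.

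**The case against.** The strongest objection is that covariate adjustment of an analysis nobody has planned is a matter of preference, and that its benefit rests on a relation found in neither document. Much of this stands. Nothing links clearance to drug level in any compartment. Participants meet "Aged 18-49 years", and low clearance is excluded, both of which narrow the covariate's range. Inverse proportionality is a steady-state idea, whereas Phase II is a single dose sampled at 4-6 hours and 24 hours. The relation need not carry over to urine, swabs or rectal tissue. Genvoya also contains components that Truvada lacks. For these reasons the covariate is suggested for blood levels only, and the arm comparison only for analytes measured in both arms.

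Three stronger readings are tempting, and the documents do not support them:

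- *The planned arm comparison loses precision by ignoring clearance.* No arm comparison is planned, so there is no precision to lose.
- *The adjustment is free, and worth ten points of power or more.* It has a cost and a break-even point. At log-level SD 0.7, a correlation of 0.5 would need a log-clearance SD of 0.35, outside the assumed range.
- *Chance imbalance in clearance is a further harm.* It is already part of the unadjusted standard error. The arms are randomised, so omitting the covariate does not cause bias.

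What the objection does not remove is the missing between-arm estimate.

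**Conclusion.** The point holds as a specification gap. The protocol sets out to compare two drugs; the SAP contains no estimate, test or interval that does so, and it assigns the screening data no analytic use. This rests on the text alone and needs no assumption.

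Naming screening creatinine clearance as a covariate is a cheap, conditional improvement on top of that. Its size depends wholly on the assumed SDs, the assumed inverse relation and 16 completers per arm. Under those assumptions the likely gain is small, and adjustment could lose slightly if the relation is weak. The change is worth making, but the arm comparison is the part that matters.

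**What to change.** Add to the SAP:

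1. Within each dosed phase (II and III), compartment and time point, and for analytes measured in both arms, compare arms on log drug level. Report the geometric mean ratio with its 95% confidence interval.
2. Where many values fall below quantification, use a rank-based comparison of the arms instead.
3. For blood drug levels, prespecify log screening creatinine clearance as a covariate and report the unadjusted ratio beside the adjusted one. State the clearance formula.
4. For men who enter a second phase, use the original screening value unless a newer one exists. The Abstract lets them skip Visit 1, the only visit where creatinine is listed, so the value will usually predate the earlier phase and the gap of at least 8 weeks.

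The cost is SAP wording and some analysis work, with no new visits, samples or participants. The statistical price of step 3 is one degree of freedom and a variance penalty of about 3-4% at 16 to 20 men per arm.

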# LAY SUMMARY

Men who have sex with men (MSM) and Transgender women (TGW) who have sex with men continue to be disproportionately affected by HIV. Over 60% of new HIV infections in the US occur among MSM. The majority of HIV infections among MSM and

TGW occur through exposure to the rectal mucosa during receptive anal intercourse (RAI). Pre-exposure prophylaxis (PrEP) is a new HIV prevention method that is recommended by CDC and WHO for MSM at risk of HIV infection. PrEP entails taking an anti-HIV medication (Truvada®; tenofovir/emtricitabine) on a daily basis to prevent HIV infection. However, current tenofovir- based regimens have shown to have side effects that researchers are hoping to reduce in newly developed anti-HIV agents. This study is designed to examine the ability of these new agents to penetrate mucosal tissues and potentially prevent HIV infection during RAI exposure for MSM and TGW.

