# Phase II

40 participants (20 in each study arm) will be enrolled in study phase 2.

Study visit 2 will occur 1-6 weeks after the screening visit. During visit 2, the study group assignment will be reviewed and participants will be provided with a single dose of Truvada® or Genvoya®. Drug will be dispensed through the Emory Investigational Drug Service. Depending on the study arm they were assigned to, MSM will be dispensed 1 day of Truvada® or Genvoya® and instructed on dosing for that day. Four to six hours after the drug is taken, a urine sample, 4 tablespoons of blood will be drawn from the participants arm, as well as, penile and urethral swabs will be collected from participants. These sample will be used at CDC to develop an assay to detect Truvada® and Genvoya® in the body. All specimens will be coded with a unique numeric identifier such that the CDC laboratories that receive the specimens will be unable to link them back to the study participants. Participants will be requested to abstain from receptive anal intercourse 3 days prior to study visit 2 and while taking study product.

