# Risks of Truvada® for PrEP

Truvada® is a combination pill that contains the medications tenofovir and emtricitabine. In clinical trials of PrEP for MSM, the drug was well tolerated. Nausea was more common among participants taking the medication than among those taking placebo (9% vs. 5%). There were no differences in severe or life-threatening adverse laboratory events between the active and placebo group. Adverse events associated with tenofovir can include a transient decrease in renal function and slight decreases in bone mineral density. Both of these effects occur with prolonged use of the medication and are not expected to occur with the limited 7-day dosing in this protocol. Nausea was more common among participants taking the medication than among those taking placebo (9% vs. 5%). There were no differences in severe or life-threatening adverse laboratory events between the active and placebo group. Adverse events associated with tenofovir can include a transient decrease in renal function and slight decreases in bone more common among participants taking the medication than among those taking placebo (9% vs. 5%). There were no differences in severe or life-threatening adverse laboratory events between the active and placebo group. Adverse events associated with tenofovir can include a transient decrease in renal function and slight decreases in bone mineral density. Both of these effects occur with prolonged use of the medication and are not expected to occur with the limited 7-day dosing in this protocol.

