### Risk of Genvoya®

Genvoya® is a combination anti-HIV medication that contains the drugs tenofovir alafenamide, emtricitabine, elvitegravir, and cobicistat. Based on clinical trials previously conducted of Genvoya®, the drug showed to be well tolerated. According to participants, the most common side effect shown was nausea with diarrhea being the second most common side effect. Of those who reported this adverse event, 0.9% and 1.5 % discontinued treatment regardless of the severity. Adverse events associated with Genvoya® can include a transient decrease in renal function and slight decreases in bone mineral density. There is also a possibility of lactic acidosis, which can be hard to identify during early stages. These effects occur with prolonged use of the medication and are not expected to occur with the limited 10-day dosing in this protocol. In contrast to Truvada®, there have been no clinical trials of Genvoya® for HIV pre-exposure prophylaxis. However, similar concerns with acquisition of HIV infection and development of HIV drug resistance as discussed above also apply to Genvoya®.

Genvoya® can also cause flare-ups in those who have hepatitis B virus. It can cause the Hepatitis B virus to suddenly return in a worse form than before if treatment was provided. For this reason, it is important that participants not participate in the study if they are known to have Hepatitis B. Nonetheless, the maximum 10 day dosing regimen for this study is unlikely to cause flare-ups in Hepatitis B even if not diagnosed.

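### The SAP has no between-arm contrast of drug levels and relates no compartment to same-visit blood, so an arm difference in mucosal levels could reflect systemic exposure rather than penetration

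*SAP*

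**What the plan says.** The protocol states its question in three places.

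- Project Description, Goal: "To compare the body compartment pharmacokinetics and mucosal inflammatory effects of" the two products.
- Lay Summary: "This study is designed to examine the ability of these new agents to penetrate mucosal tissues".
- Abstract, Design: contrasting the assay findings "between the 2 study arms will help in determining the ability of the new formulated anti-HIV drug to penetrate different body compartments".

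The SAP's analysis is one short paragraph. Its summary is "Median (range) drug levels will be calculated at baseline and each of the protocol specified follow-up time points". Its only test is a Wilcoxon signed-rank test of follow-up against baseline, judged at p < 0.05. It mentions no study arm, compartment, analyte, blood fraction or ratio.

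The protocol does not define the measured drug further; Abstract, Design refers only to concentrations of the two branded products. The risk sections show that these are not single substances. Truvada "is a combination pill that contains the medications tenofovir and emtricitabine", while Genvoya "is a combination anti-HIV medication that contains the drugs tenofovir alafenamide, emtricitabine, elvitegravir, and cobicistat".

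Blood is taken at every post-dose sampling visit: Phase II visit 2 ("4 tablespoons of blood will be drawn from the participants arm"), Phase II visit 3, and Phase III visits 3 and 4. Rectal secretions and biopsies are taken after dosing at Phase II visit 3 and Phase III visit 4.

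**The concern.** A drug level in tissue or secretions depends on how much drug circulates and on how readily it crosses into the compartment. Penetration is the second of these. If the products give different blood levels, mucosal levels will differ between arms even when penetration is the same. A real penetration difference can also be masked by an opposite difference in exposure.

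The SAP gives the reader no means of telling these apart. It plans no estimate of the arm difference on which the protocol means to rest its conclusion, and no quantity that sets a compartment against blood. Because the analyte is unnamed, the choice of which constituent to compare also stays open until the data are in hand.

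**Working it through.** **1. The plan's own figure.** Phase sizes per arm are 5, 20 and 20 (Study visits, Visit 2). 2 × (5 + 20 + 20) = 90 enrolled. With 20% non-completion (Study Population), 90 × 0.80 = 72, as the protocol states. If loss is even, each arm of Phase II or III has 20 × 0.80 = 16 completers. No power, effect size or SD is given.

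**2. Analytes.** Truvada: tenofovir, emtricitabine. Genvoya: tenofovir alafenamide, emtricitabine, elvitegravir, cobicistat. Emtricitabine is the only constituent named in both.

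**3. Mechanism.** Take tissue level = blood level × penetration. Then the arm ratio of tissue levels = f × p, where f is the arm ratio of blood levels and p the arm ratio of penetration.

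- p = 1, f = 2: tissue ratio 2, which looks like double the penetration.
- p = 1, f = 0.5: tissue ratio 0.5, which looks like half.
- p = 0.5, f = 2: tissue ratio 1, so a real difference is hidden.

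The arm ratio of compartment-to-blood ratios equals p in each case.

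**4. Illustration.** The inputs f and the log-scale SDs are assumptions. True penetration is equal in both arms. Each scenario has 4,000 simulated trials, 16 men per arm, and a two-sided rank-sum test between arms at 0.05. The SAP contains no such test; it stands in for the comparison promised in the protocol. Share of trials significant on absolute tissue level:

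| Log SD: blood / penetration | f = 1.5 | f = 2 | f = 3 |
|---|---|---|---|
| 0.4 / 0.4 | 47.0% | 88.9% | 99.8% |
| 0.5 / 0.7 | 22.5% | 55.3% | 91.4% |
| 0.5 / 1.0 | 16.0% | 36.7% | 72.4% |

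On the tissue-to-blood ratio, the share is 4.3% to 5.6% in all nine cells. With f = 1, the absolute level gives 3.7% to 4.7%. With 20 per arm and f = 2, absolute levels give 46.9% to 95.6% and the ratio about 5%.

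The multiplicative model is built into this simulation, so the results size the effect under that model and do not validate it.

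**5. Precision of the ratio.** If log tissue and log blood have equal SD σ and correlation ρ, the SD of the log ratio is σ√(2(1 − ρ)).

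- ρ = 0.3: σ√1.4 = 1.18σ
- ρ = 0.5: σ√1.0 = 1.00σ
- ρ = 0.7: σ√0.6 = 0.77σ

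Below ρ = 0.5 the ratio is noisier than the absolute level. The documents give no value for ρ.

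**The case against.** A reader might infer that the SAP tests absolute levels between arms in each compartment, so that a systemic difference will be reported as a penetration difference. The documents do not support this. The only planned test is within person, and a signed-rank test against baseline yields no arm contrast. The risk lies in the comparison that the protocol promises and the SAP leaves unspecified. It also needs an exposure difference, and the documents give no concentration data.

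A reader might also infer that absolute levels are the wrong quantity, or that no penetration conclusion can be drawn. That too is unsupported. The Goal is compartment pharmacokinetics, which absolute levels serve directly. The amount of drug present where exposure occurs is a legitimate target whatever its cause. The protocol says only that the comparison will help.

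The ratio has weaknesses of its own, and these stand:

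- Phase I has no drug, so the ratio is undefined there.
- A urine-to-blood ratio does not measure mucosal penetration.
- Swab levels need the sampled quantity to be normalised, and no method is stated.
- The products deliver tenofovir in different forms, so an arm difference in its ratio could come from the blood denominator.
- A same-time ratio assumes that the compartment tracks blood. This is doubtful 4 to 6 hours after a single dose, when only penile and urethral swabs, urine and blood are taken.

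Finally, the SAP restricts levels to no matrix, so blood medians might be reported beside tissue medians and an exposure difference would then be visible. That would help, but it gives neither an estimate of the arm difference nor its uncertainty, and it discards the within-man pairing of compartment and blood.

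**Conclusion.** The concern holds in a limited form. The planned analysis has no between-arm contrast and nothing that separates penetration from systemic exposure, although the protocol relies on a comparison between arms to inform its penetration question and already collects the blood needed. An arm difference in mucosal levels could therefore be misread.

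The size of any distortion equals the exposure ratio f under a multiplicative model. How often it would reach significance ranges from 16% (1.5-fold) to 99.8% (3-fold) in the illustration, depending on the assumed f and SDs. Nothing in the documents shows that f differs from 1. The textual gap does not depend on these assumptions. It should be closed by adding analyses; absolute levels need not be replaced.

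**What to change.** Amend the SAP before levels are compared between arms.

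1. Name each analyte, its matrix (including the blood fraction) and the rule for values below quantification.
2. **Main report.** For each analyte measured like for like in both arms, give the between-arm ratio of levels with a 95% CI at each post-dose visit in Phases II and III. Emtricitabine is the clear case.
3. **Supportive.** Beside it, analyse each man's log(compartment level / same-visit blood level), and report the between-arm ratio with a 95% CI. Do this for rectal tissue, and for secretions or swabs only where the sampled quantity is normalised. Exclude Phase I and urine. A fixed unit conversion between tissue and blood cancels in the between-arm ratio.
4. **Tenofovir.** State the measured moiety and blood matrix, and interpret its compartment-to-blood ratio cautiously because its form differs by arm.
5. Describe elvitegravir and cobicistat within the Genvoya arm only.

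The cost is analysis and SAP text; no visit or specimen is added. The supportive ratio loses men without quantifiable levels in both matrices, rests on the compartment tracking same-time blood, and with equal SDs is less precise when the correlation is below 0.5. For these reasons absolute levels remain the main report.

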# STUDY POPULATION

A total of 90 HIV-negative MSM aged 18-49 will be recruited from existing Emory University study databases of MSM who have agreed to future contact about research opportunities. We will also recruit men from community engagements events conducted by Hope Clinic recruiters, from print and on-line advertisements, and from social media advertisements. Research recruiters at the Hope Clinic and the Rollins School of Public Health are experienced in recruiting this population for research studies, including those with rectal biopsies, and do not anticipate problems. [name] is has conducted 2 similar studies before and does not anticipate any problems with recruiting the target population. Based on our previous studies, we expect approximately 20% of men will not complete all study visits, therefore the sample size of 90 men will likely result in study completion for 72 men.

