# Phase I

10 participants (5 in each study arm) will be enrolled in study phase 1.

Study visit 2 will occur 1-6 weeks after the screening visit. During visit 2, we will draw 4 tablespoons of blood from the participants arm. A urine sample as well as penile and urethral swabs will be collected from participants. These samples will be used at CDC to develop an assay to detect Truvada® and Genvoya® in the body compartments. All specimens will be coded with a unique numeric identifier such that the CDC laboratories that receive the specimens will be unable to link them back to the study participants. Finally, rigid sigmoidoscopy (described further below) will be performed and, rectal secretions will be collected with Dacron swabs, and 8-12 rectal biopsies will be collected. A rectal swab will be collected for testing for gonorrhea and chlamydia to be performed by CDC. If positive for gonorrhea or chlamydia, men will be referred for care at their private physician's office, the health department, or AID Atlanta for treatment. All men will be instructed to place nothing in the rectum and to abstain from sex for 7 days after the procedure to allow the mucosa to heal.

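### Drug levels are summarised only as median (range), with no confidence interval and no between-arm estimate, although the trial's goal is to compare the two products

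*SAP*

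**What the plan says.** The SAP has two sentences on analysis and one on significance. The description is "Median (range) drug levels will be calculated at baseline and each of the protocol specified follow-up time points". The inference is "Differences in median drug levels between baseline and study visit follow-up visits will be analyzed with non-parametric Wilcoxon-signed rank tests", followed by "A p-value of <0.05 will be considered significant". It plans no interquartile range, geometric mean, confidence interval, between-arm ratio or between-arm test, and it does not say that the summaries are split by arm.

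The protocol has no analysis section that fills these gaps. Its purpose is nevertheless comparative. The goal in Project Description is "To compare the body compartment pharmacokinetics and mucosal inflammatory effects of Truvada" against Genvoya, and the Abstract states: "Comparison of assay results between the 2 study arms will help in determining the ability of the new formulated anti-HIV drug".

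On numbers, the Phase II and Phase III paragraphs under Visit 2 give 20 men per arm in each of those phases. Study Population expects about 20% not to complete, so that "the sample size of 90 men will likely result in study completion for 72 men".

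**The concern.** The only planned test is within person, baseline against follow-up. It says nothing about Truvada against Genvoya, and it yields a p-value rather than a measure of precision. Anyone comparing the arms from the planned output therefore has only two medians and two ranges.

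A range is the smallest and largest value observed. It does not shrink as the median becomes better known. If levels are right-skewed, as drug concentrations usually are, one man sets the upper limit.

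Two misreadings are possible. A real difference between arms may look lost because the ranges overlap, and a chance difference in medians comes with nothing to show its uncertainty. In a small pharmacokinetic study the tabulated levels are close to being the main result, so this affects what the trial can conclude.

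**Working it through.** **The plan's own figure.** Men per arm: 5 + 20 + 20 = 45. Two arms: 90. Completers: 90 × (1 − 0.20) = 72, as the protocol states. No power, effect size or SD is given.

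**Inputs**
- Men per arm in a dosed phase: 20 (protocol, Phases II and III). After loss: 20 × 0.80 = 16. This assumes that the 20% loss is spread evenly over phases and arms.
- Between-person variability: not given. Assumed log-normal, with log SD s of 0.3, 0.5, 0.7 and 1.0. The CV is √(exp(s²) − 1), that is 31%, 53%, 80% and 131%.
- True arm difference: not given. Assumed 2-fold and 4-fold.

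**Formulas and method**
- Overlap of ranges: simulation of two arms of 16, at least 40,000 trials per setting, counting trials in which the maximum of the lower arm reaches the minimum of the higher arm.
- Chance ratio of two medians with no true difference (95% limit). The large-sample form is exp(1.96 × 1.253 × s × √(2/16)). At s = 0.7 the SE of one log median is 1.253 × 0.7/√16 = 0.219, the SE of the difference is 0.310, and exp(1.96 × 0.310) = 1.84. Direct simulation gives 1.79, so the approximation is slightly wide.
- Precision of a geometric mean ratio: × or ÷ exp(t × s × √(2/16)), with t = 2.042 on 30 degrees of freedom. At s = 0.7 this is exp(2.042 × 0.7 × 0.3536) = 1.66.

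**Results, 16 per arm**

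| Log SD (CV) | Ranges overlap, true 2-fold | Ranges overlap, true 4-fold | Chance ratio of medians, 95% limit (simulated) | Geometric mean ratio known to within × or ÷ |
|---|---|---|---|---|
| 0.3 (31%) | 96% | 8% | about 1.3 | 1.24 |
| 0.5 (53%) | 99.9% | 84% | 1.52 | 1.43 |
| 0.7 (80%) | 100% | 99% | 1.79 | 1.66 |
| 1.0 (131%) | 100% | 99.9% | 2.3 | 2.06 |

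At log SD 0.7, a 95% CI for the geometric mean ratio excludes 1 in 77% of trials at 2-fold and in about 100% at 4-fold. The ranges overlap in nearly all of the same trials.

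**Sensitivity.** At a CV of exactly 50% (log SD 0.47), 4-fold overlap is 78% with 16 men and 86% with 20. At a CV of 30% and a 3-fold difference it is 37% with 16 and 47% with 20.

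**Interval for one median.** With 16 men, the 4th to 13th ordered values give coverage 1 − 2 × (1 + 16 + 120 + 560)/65,536 = 97.9%. With 20 men, the 6th to 15th give 95.9%.

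**Do per-arm intervals suffice?** At log SD 0.7 and a true 2-fold difference, the two distribution-free median intervals still overlap in 87% of trials and the interquartile ranges in 70%. At 4-fold, the median intervals overlap in 17%.

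**The case against.** The strongest reply is that median (range) is a legitimate description of small skewed samples, that inference is assigned to the signed-rank test, and that nothing in the documents says arms will be judged by whether ranges overlap. This stands in part. The misreading is a risk and not a planned procedure, and there is no need to remove the range. It does not answer the gap, because the signed-rank test does not compare arms and nothing else in the plan does.

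A second reply also stands: better per-arm summaries alone would not rescue the comparison. Per-arm median intervals overlap in 87% of trials at a true 2-fold difference (log SD 0.7), so the 77% above can be credited only to a between-arm ratio.

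Three stronger readings are tempting, and the documents do not support them.
- A reader might infer that arms differing 2- to 4-fold will always show overlapping ranges. No variability is stated, and at log SD 0.3 a 4-fold difference gives overlap in only 8% of trials.
- A reader might infer that chance 2-fold differences in medians will be common. With 16 per arm they occur in 1.5% of trials at a CV of 75%, 5% at 100% and 13% at 150%.
- A reader might infer that ranges mislead because group sizes differ, since "10 participants (5 in each study arm) will be enrolled in study phase 1" while the later phases have 20 per arm. For drug levels this fails. The Lay Summary says that Phase I men receive no product, so there is no spread of drug levels to compare, and the two dosed phases are planned at equal size.

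**Conclusion.** The concern holds in conditional form. Without any assumption, the SAP's only drug-level summary carries no measure of precision, and no between-arm estimate is planned for a trial whose stated goal is a comparison of two products.

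The size rests on log-normal levels, 16 completers per arm per dosed phase, and a variability that the documents do not give. At a log SD of about 0.5 or more, ranges overlap in about 84-100% of trials when the arms differ 2- to 4-fold, and identical arms can show medians about 1.5- to 2.3-fold apart by chance. At log SD 0.3 the overlap problem remains at 2-fold and largely disappears at 4-fold.

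No summary removes the limit set by sample size. At log SD 1.0 the ratio is known only to within about 2.06-fold, so a 2-fold difference could not be reliably separated from none. An interval would show that openly, and a range would not. This is a low-cost improvement in analysis and reporting. Its most important part is the between-arm ratio.

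**What to change.** Replace the SAP's summary sentence with wording to this effect:

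- For each analyte, by arm, phase, time point and compartment, report the number of men with quantifiable drug, the median with a distribution-free 95% CI, and the interquartile range. The range may be kept alongside.
- Where nearly all values are quantifiable, add the geometric mean with 95% CI.
- In Phases II and III, for analytes measured in both arms, report the between-arm ratio with 95% CI. Use a geometric mean ratio, or a Hodges-Lehmann ratio when values fall below quantification.

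The SAP should name the analytes to which the ratio applies. The protocol's risk sections list emtricitabine in both products, but elvitegravir and cobicistat only in Genvoya, so the last two have no ratio.

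The cost is a few lines of SAP text, a little more analysis and some table space. No new data or visits are needed.
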